Red Blood Cell ATP Release and Vascular Function in Humans

NCT03404843

May 19, 2018

Fasudil Study Protocol

Using a double-blind, placebo-controlled, crossover design, subjects were randomized to receive an infusion of either saline (placebo control) or fasudil for their first experimental visit. Subjects then received the opposite treatment for their second experimental visit, with at least five days and no more than two months between the first and second visit. All experimental measures were performed in the same order for each visit within a subject, with the order of hypoxia and graded-intensity rhythmic handgrip exercise trials randomized and counterbalanced between subjects. Arterial stiffness measures (augmentation index and carotid-femoral pulse wave velocity) were performed before and after placement of the venous catheter and 60 min treatment administration. For both the hypoxia and exercise trials, resting hemodynamics were measured for 2-3 min until a steady-state was observed, after which the physiological stimulus was initiated. The hypoxia trial consisted of 3 min of steady-state hypoxia at an oxygen saturation of ~80% as assessed via pulse oximetry on the earlobe (SpO₂; plus ~2 min for the normoxia to hypoxia transition). The exercise trial consisted of 4 min at each workload to ensure that steady-state hemodynamics were achieved. Blood samples for plasma [ATP] were taken under steady-state conditions at rest, the end of hypoxia, and the end of each exercise workload.

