## Fasudil Statistical Analysis Plan

All values are reported as mean  $\pm$  SEM. All analyses were performed using R (R Core Team 2016, R Foundation for Statistical Computing, Vienna, Austria) with the lme4, lmerTest, pbkrtest, and lsmeans packages. Age (young or older), drug (saline or fasudil), condition (rest or exercise intensity or hypoxia), and age $\times$ drug $\times$ condition for three-way repeated measures or age $\times$ drug for two-way repeated measures ANOVA were treated as fixed effects. In order to account for the crossover design, subject and subject $\times$ drug were included in the model as random effects for the three-way repeated measures analyses and subject was included as a random effect for the two-way repeated measures analyses. When an interaction or main effect was found, appropriate pairwise comparisons were made and a Tukey test was included when necessary. Comparisons of variables relative to zero were tested using a one-tailed t-test, and differences in subject characteristics were tested using a two-tailed t-test. Comparisons between saline and fasudil were performed within age group and comparisons between young and old were performed within condition. Significance was set at  $P < 0.05$ .

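### Hypoxia/exercise trial order is a randomised between-subject factor, but the SAP's mixed models omit it and neither document says whether it was balanced within age group

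*Protocol*

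**What the plan says.** **Protocol, Fasudil Study Protocol.** Within a subject the order does not change between visits: "All experimental measures were performed in the same order for each visit within a subject". Across subjects it is allocated, "with the order of hypoxia and graded-intensity rhythmic handgrip exercise trials randomized and counterbalanced between subjects". Before each trial, "resting hemodynamics were measured for 2-3 min until a steady-state was observed, after which the physiological stimulus was initiated". No interval between the two trials is given, and nothing is said about counterbalancing order inside the young group, the older group or either treatment sequence.

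**SAP, Fasudil Statistical Analysis Plan.** The list of fixed effects opens "Age (young or older), drug (saline or fasudil), condition (rest or exercise intensity or hypoxia), and age" and goes on to the interactions. Subject and subject × drug "were included in the model as random effects for the three-way repeated measures analyses"; for the two-way models, "subject was included as a random effect for the two-way repeated measures analyses". Trial order is in neither list. Saline is compared with fasudil inside each age group, while "comparisons between young and old were performed within condition".

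**The concern.** Each subject has one trial order for the whole study, so order varies only between subjects, exactly as age does. The second trial follows another stimulus and falls later after the 60 min treatment administration. If either matters, subjects with different orders have different expected values for the same condition.

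The saline-fasudil difference is protected from an additive shift, because the shift is the same at both visits. The young-older difference is not. Left out of the model, order is counted as unexplained variation between subjects. If the two age groups also happen to have different order splits, part of the order effect appears as an age effect. The trial took the trouble to randomise this factor, and the planned analysis does not use it.

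**Working it through.** The documents give no sample size, SD or order effect, so there is no stated figure to reproduce. Everything below rests on assumed values, shown as ranges.

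**Inputs from the documents.** Order is constant within subject and counterbalanced between subjects (protocol). There is no order term, young-older is compared within condition, and the significance level is 0.05 (SAP; two-sided assumed).

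**Assumptions.** n = 8 to 20 per age group; an additive order effect d of 0.25, 0.5 or 1.0 SD of the values compared between subjects.

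**1. Error when order is balanced but not modelled.** A shift d carried by half the subjects adds variance d² × ½ × ½ = d²/4, so the standard error is multiplied by √(1 + d²/4). Nominal 80% power becomes Φ[(1.960 + 0.842)/√(1 + d²/4) − 1.960].

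| d | SE multiplier | Power |
|---|---|---|
| 0.25 | √1.0156 = 1.008 | 79.4% |
| 0.5 | √1.0625 = 1.031 | 77.6% |
| 1.0 | √1.25 = 1.118 | 70.7% |

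**2. Possible imbalance by age.** Suppose order was counterbalanced over all 2n subjects (n with each order) but not within age. The number k of young subjects with a given order is then hypergeometric. The young-older difference in share is (2k − n)/n, with mean 0 and SD 1/√(2n − 1).

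| n per group | SD of difference in share | P(exact balance) |
|---|---|---|
| 8 | 1/√15 = 0.26 | 38% |
| 10 | 1/√19 = 0.23 | 34% |
| 12 | 1/√23 = 0.21 | 32% |
| 20 | 1/√39 = 0.16 | 25% |

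At n = 12, a split of 8/4 versus 4/8 or worse (difference at least 1/3) has probability 22%. If order was counterbalanced within age, all these differences are zero.

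**3. Bias given the split.** Bias = d × (share in young − share in older). At n = 10:
- 6/4 versus 4/6 (difference 0.2): 0.10 SD at d = 0.5, 0.20 SD at d = 1.0.
- 7/3 versus 3/7 (difference 0.4): 0.20 SD and 0.40 SD.

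The mean difference in share is 0, so the expected bias over randomisation is 0.

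**4. Simulation of the three-way structure.** n = 10 per group, 2 drugs, 2 conditions, 6,000 runs per setting; assumed SDs 0.8 (subject), 0.3 (subject × drug) and about 0.52 (residual), total 1. The order effect was applied either to the stimulus condition only or to both conditions.

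| Order split | Bias, young-older | Type I error, d = 0.5 | Type I error, d = 1.0 |
|---|---|---|---|
| 5/5 in each group | −0.009 to 0.008 | 0.041-0.052 | 0.025-0.040 |
| Random allocation | −0.015 to 0.005 | 0.050-0.056 | 0.050-0.071 |
| 7/3 versus 3/7 | about 0.20 (d = 0.5), 0.40 (d = 1.0) | 0.066-0.072 | 0.104-0.126 |

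The saline-fasudil contrast had no bias in any setting (−0.007 to 0.005). When an effect of d = 1.0 fell on the stimulus condition only, its test became conservative (type I error about 0.03 to 0.04), because the order × condition variance goes into the residual.

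**5. Price of the order term.** With 2n − 3 instead of 2n − 2 between-subject degrees of freedom, the two-sided 5% critical value goes from 2.145 to 2.160 at n = 8 (+0.7%) and from 2.042 to 2.045 at n = 16 (+0.1%).

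**The case against.** The strongest defence is that the design already deals with this. Order is randomised, so young-older is unbiased on average. Order is the same at both visits, so the drug contrast is clean. Each stimulus waits for a steady resting state, which limits carry-over, and no carry-over is documented. At 0.25 to 0.5 SD the loss is small. All of this stands, and it sets the weight of the point. It does not remove it: a steady state can sit at a shifted level, and the later start relative to treatment administration remains.

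Five stronger readings are tempting, and the documents do not support them.
- **Order was unbalanced by age.** The protocol's wording is compatible with counterbalancing inside each age group; the documents are silent.
- **Recovery between trials was only 2-3 min.** That is the window for measuring rest before a stimulus. The interval between trials is not given.
- **One pooled rest value serves both trials.** The SAP's condition list can equally describe separate rest/exercise and rest/hypoxia analyses.
- **Every analysis is affected.** The t-tests on subject characteristics cannot depend on trial order. Arterial stiffness probably does not either, since it is timed to catheter placement and treatment administration.
- **Age × drug is biased.** That needs an order effect that differs by drug together with an unequal split by age, and the documents give no evidence for either.

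**Conclusion.** The point holds as one about precision and reporting. A factor that the trial randomised between subjects is missing from the mixed models, and it bears on the young-older comparison. The standard error of that comparison rises by 0.8%, 3% or 12% for order effects of 0.25, 0.5 or 1.0 SD, against 0.1% to 0.7% on the critical value for fitting order at n = 16 down to 8 per group. Bias is conditional: it needs both a real order effect and a different realised split in the two age groups, and it averages to zero over randomisation. The additive part of any order effect leaves the saline-fasudil estimate unbiased. Group sizes, SDs and order effects are all assumed, so the figures show scale and do not estimate what happened in this trial.

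**What to change.** For outcomes measured in or after the trials:

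1. Fit hypoxia and exercise in separate models, each with its own trial's resting value as reference, and say so in the SAP. Carry-over can reach only whichever trial came second: exercise in hypoxia-first subjects and hypoxia in exercise-first subjects. A single order term in a joint model would average over these opposite patterns.
2. Add trial order and order × condition as fixed effects (order alone where the model has no condition factor).
3. Add drug × order as a sensitivity analysis, because an order effect that differs by drug would not cancel.
4. State whether order was counterbalanced within age group, and tabulate order by age group and treatment sequence.

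No new measurements are needed, provided that each subject's allocated order was kept. The cost is one between-subject degree of freedom for order, a few within-subject degrees of freedom for the interactions, and somewhat more model specification. If there is no order effect, nothing is gained. Both documents are written in the past tense, so changing the randomisation list is probably no longer possible; the remedy in the analysis does not depend on it.

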## Fasudil Statistical Analysis Plan

All values are reported as mean  $\pm$  SEM. All analyses were performed using R (R Core Team 2016, R Foundation for Statistical Computing, Vienna, Austria) with the lme4, lmerTest, pbkrtest, and lsmeans packages. Age (young or older), drug (saline or fasudil), condition (rest or exercise intensity or hypoxia), and age $\times$ drug $\times$ condition for three-way repeated measures or age $\times$ drug for two-way repeated measures ANOVA were treated as fixed effects. In order to account for the crossover design, subject and subject $\times$ drug were included in the model as random effects for the three-way repeated measures analyses and subject was included as a random effect for the two-way repeated measures analyses. When an interaction or main effect was found, appropriate pairwise comparisons were made and a Tukey test was included when necessary. Comparisons of variables relative to zero were tested using a one-tailed t-test, and differences in subject characteristics were tested using a two-tailed t-test. Comparisons between saline and fasudil were performed within age group and comparisons between young and old were performed within condition. Significance was set at  $P < 0.05$ .

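### The crossover models have no visit (period) term, so a visit 1 to visit 2 shift costs power in saline-versus-fasudil level comparisons and biases them if treatment order is uneven within an age group

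*SAP*

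**What the plan says.** **Design.** Under Fasudil Study Protocol, "subjects were randomized to receive an infusion of either saline (placebo control) or fasudil for their first experimental visit", with the other treatment at the second visit, "with at least five days and no more than two months between the first and second visit". Counterbalancing is mentioned only for the test order within a visit: "with the order of hypoxia and graded-intensity rhythmic handgrip exercise trials randomized and counterbalanced between subjects". Treatment order is described as randomised. Nothing is said about its balance, either overall or within age group.

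**Model.** Under Fasudil Statistical Analysis Plan, the fixed effects begin "Age (young or older), drug (saline or fasudil), condition (rest or exercise intensity or hypoxia), and age" and end with the interaction of those factors (age × drug in the two-way models). The crossover is covered by the sentence that begins "In order to account for the crossover design, subject and subject" and adds subject × drug as a second random effect. For the simpler models, "subject was included as a random effect for the two-way repeated measures analyses". Neither document names a visit, period or sequence term, or a check for one.

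**Comparisons.** "Comparisons between saline and fasudil were performed within age group". The significance level is 0.05.

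**The concern.** Each subject has exactly one visit per drug, so subject × drug groups the data in the same way as subject × visit. A random effect with mean zero absorbs scatter around the drug means. It does not estimate or subtract a systematic difference between visit 1 and visit 2. In the three-way models the shift goes into the subject × drug variance, and in the two-way models into the residual. Each of these is the error term for comparing saline and fasudil levels.

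Two things are at stake. With treatment order balanced, the comparison is unbiased but conservative, and real fasudil effects are more easily missed. With order unbalanced inside an age group, part of the visit shift is read as a drug effect. Because drug comparisons are made within age group, overall balance does not protect them, and different splits in young and older subjects also distort the age × drug contrast of levels.

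**Working it through.** **Inputs from the documents:** a two-visit, two-treatment crossover with randomised first treatment; the fixed and random effects listed above; drug comparisons within age group; alpha 0.05 (taken as two-sided for the drug comparison, an assumption).

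**Inputs assumed, because the documents give none:** 12 subjects per age group; SD of the within-subject fasudil-minus-saline difference = 1; true effect τ = 0 or 0.9 SD; visit 2 minus visit 1 shift π = 0, 0.25, 0.5 or 1 SD; simple 1:1 randomisation of order. There is no sample-size or power figure in the plan to reproduce.

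**Step 1, bias.** A subject's paired difference has mean τ + π if saline came first and τ − π if fasudil came first. With n1 saline-first and n2 fasudil-first subjects, the unadjusted mean difference has bias π(n1 − n2)/n. This is 0 at 6:6, 2π/12 = 0.17π at 7:5, 4π/12 = 0.33π at 8:4 and 6π/12 = 0.5π at 9:3. The sign reverses if fasudil-first is the larger sequence.

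**Step 2, error inflation at 6:6.** The expected variance estimate rises from 1 to 1 + π²·n/(n − 1). The standard error is therefore multiplied by √(1 + π²·12/11), which is 1.03, 1.13 and 1.45 at π = 0.25, 0.5 and 1.

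**Step 3, one age group, simulated** (100,000 trials per case). The unadjusted paired t-test (11 df) is compared with the mean of the two order-specific means (10 df). In the unbalanced rows, the power figures are for a shift that opposes the drug effect.

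| Split | Type I error, no visit term (π = 0.25 / 0.5 / 1) | Power, no visit term (π = 0.25 / 0.5 / 1) | Power with visit term |
|---|---|---|---|
| 6:6 | 4.4 / 3.0 / 0.6% | 79 / 73 / 50% | 80% |
| 7:5 | 4.5 / 3.6 / 1.5% | 75 / 64 / 31% | 79% |
| 8:4 | 5.1 / 5.5 / 5.1% | 71 / 55 / 17% | 75–76% |
| 9:3 | 6.3 / 9.3 / 15.1% | 67 / 46 / 9% | 68–69% |

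With the visit term, bias is zero and type I error is 5% in every row.

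**Step 4, how likely the splits are.** With Binomial(12, 0.5) allocation, an exact 6:6 has probability 924/4096 = 23%, 8:4 or worse 1588/4096 = 39%, and 9:3 or worse 598/4096 = 15%.

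**Step 5, two-way model over both age groups** (24 subjects, pooled error, one common visit term), averaged over random splits. Power for the within-age fasudil effect, without versus with the visit term, is 85% vs 83% at π = 0, about 83% vs 83% at 0.25, 76% vs 83% at 0.5 and 55% vs 83% at 1. Averaged type I error is about 5% either way. With 8:4 in one group and 4:8 in the other, order is balanced overall, yet each within-age estimate still has a bias of 0.33π in size.

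**Step 6, age × drug contrast of levels.** Those same opposite splits give bias 0.33π − (−0.33π) = 0.67π, with type I error 8.3% at π = 0.5 and 12.0% at π = 1. A bias of 0.67π or more from any pair of splits has probability 15%.

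**Step 7, what is not exposed.** A shift common to all conditions within a visit cancels in drug × condition contrasts. Simulated bias is 0, and type I error is 4.8–5.1% at 6:6, 8:4 and 9:3. It cancels in the same way in within-visit changes such as post- minus pre-infusion arterial stiffness.

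**The case against.** The strongest reply is that the analysis remains valid under randomisation. Type I error averaged over simple randomisation is about 5%, balanced order makes the test conservative, and at 8:4 the error rate hardly moves. Marked inflation for one group needs about 9:3 together with a sizeable shift. The allocation method is unstated, so balanced order is possible. All of this stands, and it means the general harm is lost power, with bias depending on the split that occurred.

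The magnitudes are also assumptions. Nothing in either document indicates a shift of 0.5 to 1 SD, and below about 0.25 SD leaving the term out costs nothing or is slightly better. The 55% at 8:4 is the adverse direction only. With the shift helping, unadjusted power is 87.5%, so the average over directions is (55.1 + 87.5)/2 = 71%, against 75%. That is fair, although the helped case gains its power from bias.

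Finally, much of the protocol concerns responses within a visit, and the SAP's tests against zero suggest that some outcomes are change scores. Where the two-way outcomes are changes, Step 5 does not apply to them. The documents do not say which outcomes use which model, and level comparisons within age group remain exposed.

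None of this makes the subject × drug effect a substitute for a visit effect, or supplies the order counts a reader would need to judge the risk.

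**Conclusion.** The concern holds. The model as specified leaves a visit shift in the error of every saline-versus-fasudil level comparison, and in the estimate itself when order is unequal within an age group. On the assumptions above, a shift of 0.5 SD costs about 7 points of power, both in one balanced group (80% to 73%) and in the two-age model averaged over splits (83% to 76%). A shift of 1 SD costs about 30 points (80% to 50%) and 28 points (83% to 55%). Conditional bias is π(n1 − n2)/n.

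The omission is certain from the text. The realised harm is not shown, because the sample size, order split and visit shift are all unreported. With no shift, nothing is lost by the plan as written. This is a worthwhile correction to the analysis and does not show that the results are wrong.

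**What to change.** Add visit (1 or 2) as a fixed effect in both the two-way and the three-way models, and report the visit-adjusted fasudil effects. Report how many young and how many older subjects received saline first. Both documents are in the past tense, so the models must be refitted as well as the text changed; a visit-adjusted result added at this stage should be labelled as such and shown beside the planned one. A single visit term assumes the same shift in young and older subjects, which should be stated.

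No new data are needed, since visit number follows from the design. The price is one degree of freedom plus some precision when order is uneven. With no true shift, single-group power falls from 81% to 80% at 6:6, 75% at 8:4 and 68% at 9:3. In the two-age model it falls from 85% to 83% on average, with break-even at a shift of about 0.25 SD. A visit term does not address carryover, which is a separate question.

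### The three-way mixed model omits subject × condition variance; if that variance is above zero, age × condition tests are too liberal and drug × condition tests too conservative

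*SAP*

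**What the plan says.** The SAP (Fasudil Statistical Analysis Plan) takes as fixed effects "Age (young or older), drug (saline or fasudil") and "condition (rest or exercise intensity or hypoxia"), together with the three-way interaction. The random part has two terms, one for subject and one for the subject-by-drug combination; these "were included in the model as random effects for the three-way repeated measures analyses". No other random effect or covariance structure is given for the repeated conditions. The reason offered concerns the crossover only.

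On follow-up testing the SAP says "When an interaction or main effect was found, appropriate pairwise comparisons were made and a Tukey test was included when necessary".

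The protocol (Fasudil Study Protocol) says "All experimental measures were performed in the same order for each visit within a subject", and "Blood samples for plasma [ATP] were taken under steady-state conditions at rest, the end of hypoxia, and the end of each exercise workload". Each subject therefore contributes every condition under both saline and fasudil.

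**The concern.** Subjects may differ in how strongly they respond to hypoxia or exercise, and such differences may persist from one visit to the next. That is subject × condition variance. Because each subject × condition cell is observed twice, once per drug, it can be separated from the residual. The SAP model leaves it out, so it goes into the residual, where it does not belong for any of the within-subject interaction tests.

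Two things are at stake. A liberal age × condition test finds age differences in the response to the stimulus too often. A conservative drug × condition test can miss a real change in the fasudil effect across conditions. Because pairwise comparisons follow significant omnibus effects, both errors influence what is examined next.

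**Working it through.** **Inputs from the documents.** Age has 2 levels between subjects; drug has 2 levels and condition c levels within subjects; alpha is 0.05; the random effects are subject and subject × drug. I read the fixed part as full factorial. The SAP names only the main effects and the three-way term, but separate two-way interaction tests need the full factorial.

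**Inputs assumed.** The plan has no figure to reproduce: it gives no sample size, number of workloads or variance component. I assume 12 subjects per age group, equal residual variance, and variances of 1 for subject, 0.25 for subject × drug and 0.25 for residual. I take c = 2 (rest, hypoxia) and c = 4 (rest plus 3 workloads). Let r be the ratio of subject × condition variance σ²SC to residual variance σ²e, and σ²SD the subject × drug variance.

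**Expected mean squares, balanced data**

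- Subject × condition: σ²e + 2σ²SC
- Subject × drug × condition: σ²e
- Residual of the SAP model, which pools these two strata with equal df: σ²e + σ²SC

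Under the null, the numerator-to-denominator expectation for condition and age × condition is (1 + 2r)/(1 + r). For drug × condition and age × drug × condition it is 1/(1 + r). At r = 1 these are 3/2 = 1.5 and 1/2 = 0.5.

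**Size and power.** Type I errors come from 400,000 simulated sets of mean squares per scenario. Power comes from 20,000 simulated trials per scenario, for a saline–fasudil difference of one residual SD at one condition. Ranges cover c = 2 and c = 4.

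| r | Age × condition type I error | Drug × condition type I error | Drug × condition power, SAP model |
|---|---|---|---|
| 0.25 | 7.3–8.9% | 2.2–3.0% | 56–59% |
| 0.5 | 8.9–11.7% | 0.9–1.8% | 44–50% |
| 1 | 11.0–15.5% | 0.2–0.7% | 25–36% |
| 2 | 13.9–19.5% | 0.01–0.15% | 6–20% |

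With the missing term, power is 65–69%. Type I error of the omnibus interaction tests is 4.6–5.3% at r from 0.25 to 2.

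**Sensitivity.** With subject × drug variance at half the residual, c = 4 and r = 1, age × condition error is 15.5–15.7% for 8, 12 or 20 per group. With subject × drug variance at zero it is 18.2%, and drug × condition error is 0.3%. A small check by REML on simulated data (150 replicates, 10 per group, c = 4, r = 1) gave 14.7% and 0%.

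**Pairwise standard errors**

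- *Saline versus fasudil within one condition*, model SE over true SE: √[(σ²SD + σ²e + σ²SC(1 − 1/c)) / (σ²SD + σ²e)], while the subject × drug estimate stays above zero. At c = 4 and r = 1: √[(0.25 + 0.25 + 0.25 × 0.75)/0.50] = √1.375 = 1.17. Over c = 2 to 4, the SE is 3–5%, 6–9%, 12–17% and 22–32% too large at r = 0.25, 0.5, 1 and 2. The 17% becomes 26% if subject × drug variance is a quarter of the residual, and 7% if it is four times the residual.
- *Condition versus rest, averaged over drugs*: √[(1 + r)/(1 + 2r)] = 0.91, 0.87, 0.82 and 0.77, so the SE is 9%, 13%, 18% and 23% too small.
- *Little affected*: saline versus fasudil averaged over conditions (ratio 0.99–1.05), and young versus old within a condition for one drug (0.99–1.01) or averaged over drugs (0.94–1.00). The two-way age × drug models have no condition factor and are not affected.

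**The case against.** The strongest case against is that no real error has been shown. The documents give no variance components, and if σ²SC is zero the SAP model is right. This stands: the directions are certain once σ²SC is above zero, but the size is not known.

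Second, the comparisons that the SAP names are saline versus fasudil within age group and young versus old within condition. The first are calibrated or conservative and the second are close to calibrated, so an age × condition test that wrongly opens follow-up leads to contrasts that are themselves near nominal. This largely stands, with one qualification. If subject variance only equals the residual, with subject × drug variance also equal to it, the averaged-over-drugs young–old ratio at c = 4 and r = 2 is √[(1 + 0.5 + 0.5 + 0.25 + 1)/(1 + 0.5 + 0.5 + 2)] = √(3.25/4) = 0.90. The omnibus results remain miscalibrated in any case.

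Third, a main effect of condition is plausible for stimuli of this kind and could open follow-up whatever the interaction tests show. The SAP does not say which effect opens which comparison, so the harm through follow-up depends on how its rule is read. The loss of power in the drug × condition test itself does not.

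Fourth, the added term does not cure unequal residual variance and can expose it. With residual SDs of 0.5:0.75:1:1.5 over 4 conditions and r = 1, the top-workload saline–fasudil SE goes from 8% to 21% too small, and the type I error of that contrast from about 7% to about 12%. The drug × condition test goes from 0.6% to 6.8%. This stands and limits the fix: the term should not be added without looking at residual variance by condition.

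**Conclusion.** The concern holds. The SAP fixes at zero a variance that the design allows to be estimated. If that variance is positive, the condition and age × condition tests are too liberal and the drug × condition and age × drug × condition tests too conservative. Satterthwaite or Kenward-Roger degrees of freedom do not repair a missing variance component. Under the stated assumptions, even a ratio of 0.25 raises age × condition error to 7.3–8.9% and lowers drug × condition error to 2.2–3.0%.

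Under equal residual variance, the drug-side error costs power and does not create false fasudil effects. The documents name no primary outcome or hypothesis, so I do not rank the affected tests. The conclusion rests on the full-factorial reading, balanced data and equal residual variance. The omission should be corrected, but nothing here shows that any conclusion of this study is wrong.

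**What to change.** Add (1|subject:condition) to the random part of the three-way models. State whether Satterthwaite or Kenward-Roger degrees of freedom are used; the SAP lists packages but no choice. Report the estimated variance components. Check residual variance by condition; if it clearly differs, base the within-condition saline–fasudil comparisons on each condition's own paired differences, or model the variance by condition. The SAP is written in the past tense, so if the analyses are done, refit them and disclose any conclusion that changes.

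The cost is one term in existing lme4 code and no new data. Some fits may be singular; a zero estimate returns the current model. Denominator df for condition and age × condition halve: with 24 subjects in 2 groups, from 2 × 22 × 3 = 132 to 66 at 4 conditions, and from 44 to 22 at 2. If the true variance is zero, type I error is about 4.1–4.3% for age × condition and 5.7–6.1% for drug × condition.
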